Test Article(s)	Investigational Products: Biotrue ONEday and Oneday for Presbyopia and Dailies Total 1 Multifocal Contact Lenses. Control Products: None
Wear and Replacement Schedules	Wear Schedule: Daily Replacement Schedule: Daily Disposable
Objectives	Primary Objective: To evaluate the visual performance of a marketed multifocal contact lens in a population of presbyopes with myopia and hyperopia. Secondary Objective: CLUE vision score
Study Endpoints	Primary endpoints: The primary endpoints in this study are distance and near binocular high luminance, high contrast visual performance on logMAR scale. Secondary endpoint: The secondary endpoint is overall quality of vision assessed using the Contact Lens User Evaluation questionnaire (CLUE™). Other endpoint: Ease of fit as evaluated by the number of lenses used to optimize.

Study Design	
This is a single-masked, randomized, cross-over, dispensing pilot study. There will be six study visits. Visit 1 will include baseline measurements and screening to ensure eligibility. Eligible subjects will be randomized and fit in one of the study lenses and dispensed for 2-4 days. At Visit 2 additional measurements will be performed and it will be determined if lens optimization is required and lenses dispensed for an additional 6-8 days. At Visit 3 the primary endpoint data used for analysis will be collected. There will be a 4-8-day washout before the subject will be fit with the 2nd lens at Visit 4 and dispensed for 2-4 days. At Visit 5 additional measurements will be performed and it will be determined if lens optimization is required and lenses dispensed for an additional 6-8 days. At Visit 6 the primary endpoint data used for analysis will be collected.
 
See the flow chart at the end of the synopsis table for the schematic of the study visits and procedures of main observations.
				
Sample Size	
A total of approximately 80 eligible subjects will be enrolled into the study with 60 (30 myopes and 30 hyperopes) subjects targeted to complete the study. An attempt will be made to evenly distribute the subjects across the following ADD groups.
 
 
 ADD 0.75 D to 1.50 D	ADD 1.75 D to 2.50 D	
 
 30 Subjects	30 Subjects	
 
	ADD 0.75 D to 1.50 D	ADD 1.75 D to 2.50 D	30 Subjects	30 Subjects
ADD 0.75 D to 1.50 D	ADD 1.75 D to 2.50 D				
30 Subjects	30 Subjects				
Study Duration	
The study recruitment is anticipated to be approximately 3 weeks and the data collection approximately and additional 3 weeks.
				
Anticipated Study Population	
Habitual contact lens wearer who are myopic or hyperopic and have presbyopia.
				
Eligibility Criteria	
Potential subjects must satisfy all of the following criteria to be enrolled in the study:
 
 1. The subject must read, understand, and sign the STATEMENT OF INFORMED CONSENT and receive a fully executed copy of the form. 2. The subject must appear able and willing to adhere to the instructions set forth in this clinical protocol. 3. The subject must be between at least 40 years of age and not greater than 70 years of age. 4. The subject's distance spherical equivalent refraction must be in the range of +3.75 D to -3.75 D. 				

[figure not shown]
5. The subject's refractive cylinder must be ≤ -0.75 D in each eye.
6. The subject's ADD power must be in the range of $+0.75$ D to $+2.50$ D in each eye.
7. The subject must have best corrected visual acuity of 20/20⁻³ or better in each eye.
8. The subject must own a pair of wearable spectacles if required for their distance vision.
9. The subject must be an adapted soft contact lens wearer in both eyes (i.e. worn lenses a minimum of 2 days per week for at least 8 hours per wear day, for 1 month or more duration).
10. The subject must either be wearing a presbyopic contact lens correction (e.g., reading spectacles over contact lenses, multifocal or monovision contact lenses, etc.) or respond positively to at least one symptom on the "Presbyopic Symptoms Questionnaire".

Potential subjects who meet any of the following criteria will be excluded from participating in the study:

1. Ocular or systemic allergies or disease, or use of medication which might interfere with contact lens wear.
2. Pregnancy or lactation.
3. Currently diagnosed with diabetes.
4. Infectious diseases (e.g. hepatitis, tuberculosis) or an immune-suppressive disease (e.g. HIV).
5. Clinically significant (Grade 3 or 4) corneal edema, corneal vascularization, corneal staining, tarsal abnormalities or bulbar injection, or any other corneal or ocular abnormalities which would contraindicate contact lens wear.
6. Entropion, ectropion, extrusions, chalazia, recurrent styes, dry eye, glaucoma, history of recurrent corneal erosions.
7. Any previous, or planned, ocular or intraocular surgery (e.g., radial keratotomy, PRK, LASIK, lid procedures, cataract surgery, retinal surgery, etc.).
8. A history of amblyopia, strabismus or binocular vision abnormality.
9. Any ocular infection or inflammation.
10. Any ocular abnormality that may interfere with contact lens wear.
11. Use of any ocular medication, with the exception of rewetting drops.
12. History of herpetic keratitis.
13. Participation in any contact lens or lens care product clinical trial within 30 days prior to study enrollment.

	14. Employee of clinical site (e.g., Investigator, Coordinator, Technician)
Disallowed Medications/Interventions	Any systemic medications that may affect contact lens wear and any ocular medications with the exception of rewetting drops. Previous ocular or intraocular surgery.
Measurements and Procedures	The key assessments for this study will be distance and near binocular high luminance, high contrast visual performance on logMAR scale and overall quality of vision assessed using the Contact Lens User Evaluation questionnaire (CLUE™).
Microbiology or Other Laboratory Testing	None
Study Termination	The occurrence of one or more Unanticipated Adverse Device Effect (UADE), or any SAE where relationship to study agent cannot be ruled out, will result in stopping further dispensing investigational product. In the event of a UADE or SAE, the Sponsor Medical Monitor may unmask the treatment regimen of subject(s) and may discuss this with the Principal Investigator before any further subjects are enrolled.
Ancillary Supplies/ Study-Specific Materials	ETDRS light box and logMAR High Contrast and Low Contrast 3M charts, Guillon-Poling Near Charts, Desk lamps, Chart holder, Sekonic light meter, Pupillometer, Contact lens cases, and Eye-Cept® rewetting drops.
Principal Investigator(s) and Study Institution(s)/Site(s)	A full list of Principal Investigators, clinical sites, and institutions is kept separately from the Study Protocol and is included in the study Trial Master File.

Figure 1: Flowchart

COMMONLY USED ABBREVIATIONS AND DEFINITIONS OF TERMS

ADD	Plus Power Required for Near Use
ADE	Adverse Device Effect
AE	Adverse Event/Adverse Experience
BCVA	Best Corrected Visual Acuity
BSCVA	Best Spectacle Corrected Visual Acuity
CFR	Code of Federal Regulations
CLUE	Contact Lens User Experience
CLDEQ-8	8-Item Contact Lens Dry Eye Questionnaire
COAS	Complete Ophthalmic Analysis System
COM	Clinical Operations Manager
CRA	Clinical Research Associate
CRF	Case Report Form
CRO	Contract Research Organization
CT	Center Thickness
CTP	Clinical Technical Procedure
D	Diopter
DMC	Data Monitoring Committee
eCRF	Electronic Case Report Form
EDC	Electronic Data Capture
ETDRS	Early Treatment Diabetic Retinopathy Study
FDA	Food and Drug Administration
GCP	Good Clinical Practice
HIPAA	Health Insurance Portability and Accountability Act
HIV	Human Immunodeficiency Virus
IB	Investigator's Brochure
ICF	Informed Consent Form
ICH	International Conference on Harmonization
IDE	Investigational Device Exemption
IEC	Independent Ethics Committee
IRB	Institutional Review Board
IRT	Item Response Theory
ISO	International Organization for Standardization
ITT	Intent-to-Treat
JJVC	Johnson & Johnson Vision Care, Inc.
LC	Limbus Center
LogMAR	Logarithm of Minimal Angle of Resolution
MedDRA [®]	Medical Dictionary for Regulatory Activities
MOP	Manual of Procedures
NIH	National Institutes of Health
OD	Right Eye
OHRP	Office for Human Research Protections
OHSR	Office for Human Subjects Research
OS	Left Eye
OU	Both Eyes
PD	Protocol Deviation

PHI	Protected Health Information
PI	Principal Investigator
PIG	Patient Instruction Guide
PQC	Product Quality Complaint
PRO	Patient Reported Outcome
QA	Quality Assurance
QC	Quality Control
SAE	Serious Adverse Event/Serious Adverse Experience
SAP	Statistical Analysis Plan
SAS	Statistical Analysis System
SD	Standard Deviation
SOP	Standard Operating Procedure
UADE	Unanticipated Adverse Device Effect
USADE	Unanticipated Serious Adverse Device Effect
VA	Visual Acuity

1. INTRODUCTION AND BACKGROUND

Johnson & Johnson Vision recently launched a daily disposable multifocal contact lens, 1-Day ACUVUE® Brand MOIST® Multifocal. Since the launch of this lens additional daily disposable multifocal contact lenses have been approved and marketed. The purpose of this clinical study is to evaluate the performance of two of the newer competitor lenses that have been launched. The data will help to better understand the performance strengths and weaknesses of each product.

1.1. Name and Descriptions of Investigational Products

This study will test two (2) marketed multifocal contact lenses, Biotrue ONEday® for Presbyopia and Dailies Total 1® Multifocal Contact Lens. Further details about the test articles are found in Section 6 of this protocol.

1.2. Intended Use of Investigational Products

The intended use of the lenses is to correct distance spherical refractive error and presbyopia. Greater details on each of the marketed products can be found in the package insert in the appendices of this protocol.

1.3. Summary of Findings from Nonclinical Studies

Not Applicable – Marketed product only.

1.4. Summary of Known Risks and Benefits to Human Subjects

The contact lenses are currently marketed products that, like all multifocal contact lenses, act as a refractive media to correct for distance spherical refractive error and presbyopia. Beyond having their vision corrected by the contact lenses the subject will have no direct benefit from participating in the study.

The intent of these products is for use as a daily disposable contact lens that the subject wears while awake. The lenses are not intended for extended wear or reuse. This evaluation is for daily disposable modality only. Anticipated risks and adverse reactions with this lens are like other soft daily wear contact lenses used to correct presbyopia. A listing of examples of adverse reactions is found in the Section 13 of this protocol. The Investigator should follow normal clinical guidelines regarding examination and care of subjects who participate in this trial. For the most comprehensive clinical information regarding the marketed products refer to the package insert for the marketed product locate in the appendices of this clinical protocol.

1.5. Relevant Literature References and Prior Clinical Data Relevant to Proposed Clinical Study

A PubMed literature search using the term “Biotrue Oneday for Presbyopia” and “Dailies Total 1 Multifocal Contact Lens” revealed no results. Additional information regarding the marketed products can be found in the package inserts located in the appendices of this clinical protocol.

2. STUDY OBJECTIVES, ENDPOINTS AND HYPOTHESES

2.1. Objectives

Primary Objective:

To evaluate the visual performance of a marketed multifocal contact lens in a population of presbyopes with myopia and hyperopia.

Secondary Objective:

CLUE vision score

Exploratory Objective: Not Applicable

2.2. Endpoints

Primary Endpoint

The primary endpoint in this study are distance and near binocular high luminance, high contrast visual performance on logMAR scale.

Secondary Endpoint

The secondary endpoint is overall quality of vision assessed using the Contact Lens User Evaluation questionnaire (CLUE™). CLUE is a validated Patient Reported Outcome (PRO) questionnaire developed to measure general and throughout the day comfort/vision, as well as symptoms of discomfort/poor vision, lens handling and packaging. Derived CLUE scores using Item Response Theory (IRT) follow a normal distribution with a population average score of 60 (SD 20), where higher scores indicate a more favorable/positive response. A 5-point increase in an average CLUE score translates into 10% shift in the distribution of scores for population of soft contact lens wearers. Both primary and secondary endpoints will be assessed after wearing each optimized study lens for 6-8 days.

Other Observations:

The other endpoints are the ease of fit as measured by the total number of lenses required to optimize vision each lens type and the ocular physiological response are measured by the average corneal staining grade using the FDA biomicroscopy scale for corneal staining. The data for the ease of fit and corneal staining will be summarized.

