3.3. Exclusion Criteria

Potential subjects who meet any of the following criteria will be excluded from participating in the study:

1. Ocular or systemic allergies or disease, or use of medication which might interfere with contact lens wear.
2. Pregnancy or lactation.
3. Currently diagnosed with diabetes.
4. Infectious diseases (e.g. hepatitis, tuberculosis) or an immune-suppressive disease (e.g. HIV).
5. Clinically significant (Grade 3 or 4) corneal edema, corneal vascularization, corneal staining, tarsal abnormalities or bulbar injection, or any other corneal or ocular abnormalities which would contraindicate contact lens wear.
6. Entropion, ectropion, extrusions, chalazia, recurrent styes, dry eye, glaucoma, history of recurrent corneal erosions.
7. Any previous, or planned, ocular or intraocular surgery (e.g., radial keratotomy, PRK, LASIK, lid procedures, cataract surgery, retinal surgery, etc.).
8. A history of amblyopia, strabismus or binocular vision abnormality.
9. Any ocular infection or inflammation.

10. Any ocular abnormality that may interfere with contact lens wear.
11. Use of any ocular medication, with the exception of rewetting drops.
12. History of herpetic keratitis.
13. Participation in any contact lens or lens care product clinical trial within 30 days prior to study enrollment.
14. Employee of clinical site (e.g., Investigator, Coordinator, Technician)

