1.12	Pupillometry	The pupil measurements will be performed OD and OS under bright illumination (7.3-7.9 EV) and dark illumination (≤ 0 EV) using a Neuroptic Pupillometer or similar instrument. The room illuminance will be measured for each condition using the Sekonic lightmeter or similar instrument.	████████
1.13	Keratometry	Keratometry will be performed OD and OS recording the steep and flat dioptric power, corresponding meridians and clarity of mires.	████████
1.14	Subjective Sphero-cylindrical Refraction	An optimal, binocular balanced distance sphero-cylindrical refraction will be performed. Record the refraction and distance visual acuity to the nearest letter. Note: Best distance visual acuity with sphero-cylindrical refraction must be at least 20/20⁻³ in each eye for the subject to enroll in the study.	████████
1.15	Near ADD Determination	The near reading addition will be determined using the binocular crossed cylinder technique at 40 cm followed by optimization in a trial frame in step 1.17 below.	████████
1.16	Ocular Dominance	Determine the distance ocular dominance with the best distance correction in place using a +1.00-blur test. If the results are equivocal use the sighting dominance test to determine the dominant eye used for the study	Appendix E
1.17	Add Refinement	Place the BCC result in the trial frame and refine the near prescription with trial lenses (or flippers) under binocular conditions.	████████
1.18	Near Visual Acuity	Using the ETDRS 2000 Series Chart 1 or 2 near card placed at 40 cm. Record the near visual acuity OD, OS and OU at 40 cm.	

1.19	Biomicroscopy	
FDA Slit Lamp Classification Scale will be used to grade the findings and determine eligibility.
 
For the conjunctival redness (██████████) 0.5 unit increments will be used in the grading. Corneal Staining Assessment (██████████) will be graded in 1.0 increments.
 
If the clearance of the fluorescein needs to be expedited, preservative-free rewetting drops or saline may be instilled.
	██████████ ██████████ ██████████
1.20	Eligibility after Baseline	
All responses to Inclusion Criteria questions must be answered “yes” and all responses to Exclusion Criteria questions must be answered “no” for the subject to be considered eligible.
 
Determine whether the subject is eligible to participate in the study based on the examination findings. If so, proceed to lens fitting. If not, complete the final evaluation and discharge the subject.
	

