- Endophthalmitis
- Hypopyon
- Hyphemia
- Penetration of Bowman's Membrane
- Persistent Epithelial Defect
- Limbal cell Damage leading to Conjunctivalization

Significant Adverse Events – Those events that are usually symptomatic and warrant discontinuation (temporary or permanent) of the test article (excluding Serious Adverse Events).

Diagnoses and conditions that are considered Ocular Significant Adverse Events include, but not limited to the following:

- Contact Lens Induced Peripheral Ulcer (CLPU)
- Significant Infiltrative Events (SIE)
- Superior Epithelial Arcuate Lesions (SEALs)
- Any Temporary Loss of >2 Lines of BSCVA
- Other Grade 3 or higher corneal findings, such as abrasions or edema
- Non-contact lens related corneal events - e.g. Epidemic Keratoconjunctivitis (EKC)
- Asymptomatic Corneal Scar
- Any corneal event which necessitates temporary lens discontinuation >2 weeks

Non-Significant Adverse Events – Those conditions that are usually asymptomatic and usually do not warrant discontinuation (temporary or permanent) of the test article. However, the Investigator may choose to treat as a precautionary measure.

Diagnoses and conditions that are considered Ocular Non-Significant Adverse Events include, but not limited to the following:

- Non-significant Infiltrative Event (NSIE)
- Contact Lens Papillary Conjunctivitis (CLPC)
- Superficial Punctate Keratitis (SPK)
- Conjunctivitis: Bacterial, Viral, Allergic
- Blepharitis
- Meibomianitis
- Contact Dermatitis
- Localized Allergic Reactions
- Any corneal event not explicitly defined as serious or significant adverse event, which necessitates temporary lens discontinuation < 2 weeks

Adverse Device Effect (ADE) – A sub-set of AEs, and include only those adverse events that are cause by or related to the investigational device.

Unanticipated Adverse Device Effect (UADE) – Any serious adverse effect on health or safety or any life-threatening problem or death caused by, or associated with, the test article, if that effect, problem, or death was not previously identified in nature, severity, or degree of incidence in the investigational plan, Investigator’s Brochure or protocol, or any other unanticipated serious problem associated with the test article that relates to the rights, safety and welfare of subjects.

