13.3. Documentation and Follow-Up of Adverse Events

The recording and documenting of adverse events (ocular and non-ocular) begins when the subjects are exposed to the test article, study treatment or study procedure. Adverse events reported before the use of test article, start of study treatment, or study procedures will be recorded as medical history. However, if the condition deteriorates at any time during the study it will be recorded and reported as an AE. Untoward medical events reported after the subject’s exit from the study will be recorded as adverse events at the discretion of the Investigator.

Upon finding an adverse event, the Principal Investigator will document the condition in the subject record and in the eCRFs. He/she will complete the Adverse Event /eCRF.

Complete descriptions of all adverse events must be available in the subject record. All Adverse Events including local and systemic reactions not meeting the criteria for “serious adverse events” shall be captured on the appropriate case report form or electronic data system. All adverse events occurring while the subject is enrolled in the study must be documented appropriately regardless of relationship.

It is the Investigator's responsibility to maintain documentation of each reported adverse event. All adverse events will be followed in accordance with applicable licensing requirements. Such documentation will include the following:

- Adverse event (diagnosis not symptom)
- Drawings or photographs (where appropriate) that detail the finding (e.g., size, location, and depth, etc.)
- Date the clinical site was notified
- Date and time of onset
- Date and time of resolution
- Adverse event classification, severity, and relationship to test articles, as applicable
- Treatment regimen instituted, including concomitant medications prescribed, in accordance with applicable licensing requirements
- Any referral to another health care provider if needed
- Outcome, ocular damage (if any)
- Likely etiology
- Best corrected visual acuity at the discovery of the event and upon conclusion of the event

In addition, if an infiltrate(s) is present, he/she will complete the Corneal Infiltrate Assessment /eCRF. Where necessary, a culture of the corneal lesion will be collected to determine if the infection is microbial in nature. If cultures are collected, the date of culture collection and laboratory utilized will be recorded.

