14. STATISTICAL METHODS

14.1. General Considerations

All data summaries and statistical analyses will be performed using the SAS software Version 9.4 (SAS Institute, Cary, NC). Throughout the analysis of data, the results for each subject/eye will be used when available for summarization and statistical analysis. Unscheduled visits will be summarized separately and will be excluded from the statistical analysis.

Summary tables (Descriptive statistics and/or frequency tables) will be provided for all baseline variables, efficacy variables and safety variables as appropriate. Continuous variables will be summarized with descriptive statistics (n, mean, standard deviation (SD), median, minimum and maximum). Frequency count and percentage of subjects or eyes within each category will be provided for categorical data.

Summaries will be presented by study lens type and will be performed separately by completion status. All analyses will be conducted on per-protocol population (see section 14.3).

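### The one ocular-physiology endpoint is an average of an ordinal staining grade, which cannot show how many eyes reach the protocol's own Grade 3 threshold

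*Combined protocol and SAP*

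**What the plan says.** Section 2.2, under other observations, states that "the ocular physiological response are measured by the average corneal staining grade using the FDA biomicroscopy scale for corneal staining". It adds: "The data for the ease of fit and corneal staining will be summarized". No hypothesis, margin or test is attached to staining.

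In Section 7.2, biomicroscopy is done at all six visits, and staining "will be graded in 1.0 increments". Visits 1 and 4 are the baselines of the two lens periods. Visits 2, 3, 5 and 6 follow dispensing of a study lens.

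Section 3.3, criterion 5, excludes subjects with "Clinically significant (Grade 3 or 4) corneal edema, corneal vascularization, corneal staining" and other listed findings, so Grades 0 to 2 are not excluded by that criterion. Section 13.1 lists among ocular significant adverse events "Other Grade 3 or higher corneal findings, such as abrasions or edema".

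Section 14.1 promises n, mean, SD, median, minimum and maximum for continuous variables, and counts and percentages of subjects or eyes for categorical data, by lens type. It does not say which kind staining is. It also says: "Unscheduled visits will be summarized separately and will be excluded from the statistical analysis". Summaries are to be made separately by completion status, while all analyses use the per-protocol set. Section 14.3 limits that set to subjects who completed every visit without substantial deviation. It also defines a Safety Population, to which Section 14 assigns no analysis.

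**The concern.** The protocol places the clinically important part of the staining scale in its upper tail, but the named endpoint describes the centre of the distribution. Where most eyes are at Grade 0 or 1, a few high grades barely move a mean, and a larger number of trivial grades moves it just as far. The unit matters too. If readings are first averaged over a subject's eyes or visits, a single high grade is diluted before it reaches any table.

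The analysis set adds to this. Section 8.2 withdraws a subject whose significant adverse event stops lens wear. That subject cannot be a per-protocol completer, so the eyes of most interest may be the ones left out.

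Section 1 gives the purpose as understanding the strengths and weaknesses of each product, and Section 14.2 says the data will inform future trials. An ocular-response figure that cannot give the rate of clinically significant staining serves neither aim well.

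**Working it through.** The documents give no staining rate, SD or margin, so there is no planned figure to reproduce. The grade distributions below are assumptions chosen to show what the summary can and cannot distinguish.

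**Inputs.** 60 completers (Section 14.2); both lenses worn bilaterally in a 2x2 crossover (Section 5.1), so 60 × 2 = 120 eyes per lens; whole grades (Section 7.2); clinical significance at Grade 3 or 4 (Section 3.3).

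**1. The mean alone.** Mean = sum of grades / 120; all eyes not mentioned are at Grade 0.
- 36 eyes at Grade 1: 36 × 1 / 120 = 0.30, with 0% at Grade 3.
- 12 eyes at Grade 3: 12 × 3 / 120 = 0.30, with 12/120 = 10% at Grade 3.
- One subject with both eyes at Grade 3 instead of Grade 0 moves the mean by 6/120 = 0.05.

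In this pair the maximum promised for continuous data does differ (1 against 3).

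**2. Adding the median and maximum.**

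| Eyes per lens | Mean | Median | Maximum | SD | Grade 3 |
|---|---|---|---|---|---|
| 12 at Grade 3 | 36/120 = 0.30 | 0 | 3 | 0.90 | 12/120 = 10% |
| 1 at Grade 3, 33 at Grade 1 | (3 + 33)/120 = 0.30 | 0 | 3 | 0.51 | 1/120 = 0.8% |

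SD = √[(sum of squares − 120 × 0.30²)/119]. The first row gives √[(108 − 10.8)/119] = 0.90, the second √[(42 − 10.8)/119] = 0.51. Only the SD separates the two rows.

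**3. Adding the SD.** Even the full continuous set does not fix the count.
- 5 eyes at Grade 3 and 21 at Grade 1: sum 15 + 21 = 36; sum of squares 45 + 21 = 66.
- 1 eye at Grade 3, 12 at Grade 2 and 9 at Grade 1: sum 3 + 24 + 9 = 36; sum of squares 9 + 48 + 9 = 66.

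Both have mean 0.30, SD √[(66 − 10.8)/119] = 0.68, median 0, minimum 0 and maximum 3. The Grade 3 shares are 5/120 = 4.2% and 1/120 = 0.8%.

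**4. The averaging unit.** One Grade 3 reading averaged with zeros becomes 3/2 = 1.5 over two eyes, or 3/4 = 0.75 over two eyes at two visits. The maximum is then diluted as well.

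**5. The analysis set.** Suppose 6 of 120 eyes reach Grade 3 and the rest are at 0: the mean is 18/120 = 0.15, with 5% at Grade 3. If those 6 eyes belong to withdrawn subjects, the remaining 114 eyes have mean 0 and no Grade 3.

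**6. What a count would deliver.** With 60 subjects, the chance of at least one affected subject is 1 − (1 − p)^60, which is 45%, 70% and 95% for p = 1%, 2% and 5%. With none observed, the one-sided 95% upper bound is 1 − 0.05^(1/60) = 4.9%. The count is readable but still imprecise.

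**The case against.** Several stronger readings are tempting, and the documents do not support them.

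- **That staining is the trial's only ocular-safety measure.** It is the only ocular-physiology item in the endpoint list. Section 13.1 separately defines ocular serious, significant and non-significant events, and Section 13.3 requires that "All adverse events occurring while the subject is enrolled in the study must be documented appropriately regardless of relationship". Symptoms and slit-lamp findings are also recorded throughout.
- **That a harmful and a harmless lens would look identical in the report.** They could share a mean. Section 14.1 also promises either SD and maximum or category frequencies. If staining is treated as categorical and tabulated by eye, the rate problem largely disappears. The text leaves that open, and the word average in Section 2.2 points the other way.
- **That unscheduled findings are lost.** Section 7.3 requires slit-lamp findings at those visits, and Section 14.1 summarizes them separately. No inferential analysis of staining exists from which they could be excluded.
- **That Grade 3 staining is defined as a significant adverse event.** The Section 13.1 entry covers Grade 3 or higher corneal findings but does not name staining. If staining is included, each case is reportable within 24 hours and is not hidden. If it is not, the adverse event record offers less protection.
- **That entry staining distorts the lens comparison.** In a crossover the same subjects wear both lenses, which blunts this point. A shift from baseline is still the clearer display.

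It is also fair to say that the staining procedure in Appendix I is redacted and may define the averaging unit, and that this is a pilot of marketed lenses with no decision rule on staining.

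What stands is that Section 2.2 names the weaker summary, Section 14.1 does not commit to the better one, and Section 14 assigns neither staining nor adverse events to the Safety Population.

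**Conclusion.** The point holds in a limited form. The named endpoint cannot report the rate of staining at the protocol's own threshold: lenses with 10% and 0.8% of eyes at Grade 3 can share mean, median and maximum, and lenses with 4.2% and 0.8% can share every continuous statistic promised. These figures rest on assumed distributions and on eye-level averaging over 120 eyes per lens. They show what is possible, not what is likely. The per-protocol restriction can remove affected subjects altogether if it is meant to cover descriptive summaries. A reader might infer that withdrawn subjects' data certainly vanish, but the commitment to summarize by completion status may preserve them in a separate table. The two statements need reconciling. Because staining is descriptive and adverse events are recorded separately, this should be corrected but does not threaten the trial's primary conclusions.

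**What to change.** In Sections 2.2 and 14.1:

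- Summarize corneal staining by lens as the number and percentage of subjects and of eyes at each worst post-dispensing grade, and at Grade 3 or higher, including unscheduled visits.
- Use the Safety Population, and attribute each reading to the lens period in which it was taken.
- Add a shift table from that period's baseline (Visit 1 or Visit 4).
- Keep the average only as a descriptive line, and state whether it is over eyes, visits or both.
- Reconcile the per-protocol restriction on all analyses with the separate summaries by completion status, and state which applies to safety variables.

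The cost is a few extra tables from data already collected, with no change to any visit, procedure or clinical rule. Worst-grade figures will look slightly less favourable than averages. Eyes with extra visits have more chances of a high worst grade, so a companion table limited to scheduled visits would let readers judge that effect.
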